1.5 Rationale for Clinical Study

Delirium occurs in at least 40%, and up to 73%, of patients undergoing HSCT.^{10,11} Delirium is associated with longer length of stay,⁴ increased mortality,⁵ impaired activities of daily living,⁶ and can have profound immediate and long-term effects on mental health with studies demonstrating lasting symptoms of depression,⁷ post-traumatic stress,⁸ and impaired cognition.⁹

Thiamine deficiency is an underappreciated cause of delirium. Thiamine deficiency has been reported in 100% of patients undergoing HSCT.¹⁷ The co-occurrence of delirium and thiamine deficiency in HSCT is not known, but in cancer patients more broadly thiamine deficiency occurred in 55% of patients, 80% of whom demonstrated some mental status abnormality.¹⁶ There are not sufficient data to support a specific dosing strategy for thiamine repletion to target delirium due to thiamine deficiency in any patient population,²⁶ and no published studies investigating treatment or prophylaxis of delirium due to thiamine deficiency in HSCT patients.

In this double-blind, randomized controlled trial, we examine the use of high dose IV thiamine to prevent occurrence and decrease severity and duration of delirium. Our study design also allows for additional novel data on the temporal relationship between thiamine deficiency and delirium in HSCT patients.

2.0 STUDY OBJECTIVES

2.1 Primary Objectives

2.1.1 To compare delirium incidence between recipients of high dose IV thiamine and placebo during hospitalization for allogeneic HSCT.

2.2 Secondary Objectives

2.2.1 To compare delirium severity between recipients of high dose IV thiamine and placebo during hospitalization for allogeneic HSCT.

2.2.2 To compare delirium duration between recipients of high dose IV thiamine and placebo during hospitalization for allogeneic HSCT.

2.2.3 To determine if thiamine status is predictive of subsequent delirium onset.

2.2.4 To investigate the effects of high dose IV thiamine on long-term health-related quality of life (HRQOL), functional status, depression, post-traumatic stress symptoms, and cognitive functioning in patients who undergo HSCT.

3.0 Criteria for Evaluation / Study Endpoints

3.1 Primary Endpoint

Delirium incidence will be defined as: DRS > 12. Delirium rating scales will be performed at baseline (prior to transplant) and then three times weekly from day after transplant to 30 days after transplant or discharge, whichever comes first.

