1.0 BACKGROUND AND RATIONALE

1.1 Study Synopsis

This is a randomized double-blind controlled trial in participants undergoing allogeneic hematopoietic stem cell transplantation (HSCT) to determine if high dose intravenous (IV) thiamine can prevent delirium and minimize the deleterious impact of delirium on health-related quality of life (HRQOL), functional status, and other neuropsychiatric outcomes. We will recruit 60 evaluable patients scheduled for allogeneic HSCT at UNC, randomize them to treatment with high dose IV thiamine (n = 30) versus placebo (n = 30), and systematically evaluate all participants for delirium and related comorbidities. We will use the Delirium Rating Scale (DRS) to measure the severity and duration of delirium immediately prior to transplant and after HSCT until 30 days post-transplant or discharge. We will obtain thiamine levels and other laboratory parameters associated with delirium the day after transplant, and continue to monitor thiamine levels weekly thereafter. We will also monitor HRQOL (FACT-BMT), functional status (ECOG-PS), depression (PROMIS-D), post-traumatic stress symptoms (PTSS-14), and cognitive function (MOCA) prior to transplant and at one, three, and six months after transplant to elucidate the persistent impact of delirium in this population and the potential for thiamine to mitigate these negative outcomes.

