7.0 EVALUATIONS AND ASSESSMENTS

7.1 Time and Events Table

	Baseline (Pre- Transplant)	Post-Transplant Day 1	Post-Transplant Days 2 – 30	F1 ^c	F2	F3
Informed Consent	•					
Group Assignment	•					
Demographic Data Form	•					
Cancer History Form	•					
Delirium Risk Factor Form	•	•	•			
Concurrent CNS Active Medication Tracking Form	•	•	•			
Baseline Labs ^a		•				
Thiamine Levels ^b		•	•			
FACT-BMT ^c	•			•	•	•
PROMIS-D ^c	•			•	•	•
PTSS-14 ^c	•			•	•	•
MOCA ^c	•			•	•	•
ECOG-PS ^c	•			•	•	•
DRS ^d	•	•	•			
Adverse Events Form		•	•			

- a. Complete Blood Count (CBC), Comprehensive Metabolic Panel (CMP), Magnesium (Mg), Phosphorus (Phos)
- b. Thiamine levels will be drawn on post-transplant day 1, 8 days post-transplant, 15 days post-transplant, 22 days post-transplant, and 29 days post-transplant.
- c. FACT-BMT, PROMIS-D, PTSS-14, MOCA, and ECOG-PS will be performed at baseline (pre-transplant) and at one (F1), three (F2), and six months (F3) after transplant.
- d. DRS will be performed at baseline, on post-transplant day 1, and three times weekly thereafter. If a participant is identified as having delirium, assessments will increase to daily until delirium resolves at which point frequency will resume at three times weekly. For participants who develop delirium during the inpatient phase, DRS will be performed at one (F1), three (F2), and six months (F3) after transplant.

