7.2 Pre-Study (Baseline) Assessments

Patients scheduled for admission to the UNC Bone Marrow Transplant unit will be considered for enrollment in this trial. Prior to transplant, the clinical research assistant (CRA) will review the trial with the subject, obtain informed consent, and the subject will complete self-report assessments for depression (PROMIS-D), post-traumatic stress symptoms (PTSS-14), and HRQOL (FACT-BMT), as well as clinician-rated assessments of cognition (MOCA), functional status (ECOG-PS), and for delirium (DRS). See Appendices A – F. The CRA or investigators will also conduct a review of electronic medical records to obtain baseline information regarding delirium risk factors, the subject's cancer and cancer treatment, and demographic information.

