7.3 Randomization

If the patient meets all inclusion/exclusion criteria, provides informed consent, and is not delirious ($DRS \leq 12$), the subjects will then be randomized in a 1:1 ratio to the intervention or control arms in a double-blind fashion such that the investigators, biostatistician, CRA(s), nursing staff, and subjects will not know which agent is being administered. The statistician of record will design a block randomization scheme, stratified by age (<65 or ≥ 65) and baseline cognitive function ($MOCA >25$ or ≤ 25), both well-known risk factors for delirium. This information will be provided to UNC Investigational Drug Services, who will manage the actual assignment of subjects to each arm using the randomization list designed by the statistician.

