7.11 Assessment of Efficacy

In order to be considered evaluable for efficacy, patients must:

- receive all 7 days of the treatment; a patient must receive at least 17/21 (80%) thiamine doses
- have delirium assessed at least weekly until one of the following is met:
 1. The participant is found to be delirious (DRS>12)
 2. The participant is at least 30 days post-transplant
 3. The participant is discharged

If a patient is deemed not evaluable, they will be replaced by a new patient. However, if a patient develops delirium during the intervention, they will still

receive the full 7 day course, not be replaced, and included in the efficacy analysis.

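### Delirium already present before the first infusion counts as a primary event, because freedom from delirium is confirmed only before randomisation and the day-1 DRS is not placed before dosing

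*Combined protocol and SAP*

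**What the plan says.** - **Check for delirium at entry.** Under section 7.3 a patient is randomised if he or she meets the criteria, "provides informed consent, and is not delirious", meaning a DRS of 12 or less. The table in 7.1 places both the baseline DRS and group assignment in the pre-transplant column.
- **Timing of that check.** The synopsis (1.1) says the DRS will "measure the severity and duration of delirium immediately prior to transplant and after HSCT". Section 3.1 says only that the baseline rating comes before transplant. Neither gives a number of days. Section 4.1.1 accepts a planned admission, and 7.2 states: "Patients scheduled for admission to the UNC Bone Marrow Transplant unit will be considered for enrollment in this trial".
- **First dose.** Section 5.2 starts study drug on the day after transplant.
- **Endpoint.** Section 3.1: "Delirium incidence will be defined as: DRS > 12", with ratings "three times weekly from day after transplant to 30 days after transplant or discharge, whichever comes first". It sets no condition on when the delirium began.
- **Day-1 rating.** The footnote to 7.1: "DRS will be performed at baseline, on post-transplant day 1, and three times weekly thereafter". Neither this footnote nor 7.4 says whether the day-1 rating comes before or after the first infusion. Section 5.9.1 says the DRS covers a 24-hour period.
- **Evaluability.** Sections 7.11 and 9.1 ask for 17 of 21 doses and weekly ratings. Neither asks that the patient be free of delirium at the first dose. Section 7.11 keeps a patient in the analysis "if a patient develops delirium during the intervention" and does not mention delirium that begins between randomisation and dosing.
- **Existing rule on onset.** Section 9.3 leaves out patients whose delirium began before treatment ended, but only in the thiamine-level analysis.

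**The concern.** The trial asks whether thiamine prevents delirium. A patient who scores above 12 on day 1 before any study drug has been given, or whose day-1 score reflects symptoms from the preceding hours, cannot have had that episode prevented. The protocol does not say outright that such a patient is an event. It follows from the endpoint definition, the day-1 rating and the absence of any exclusion.

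These cases fall equally on both arms in expectation. They add the same number of unavoidable events to each and pull the two rates together. The design has no spare power to absorb this, since 30 per group is the number that just gives 80%. The estimate is affected too: section 9.2 offers it as the basis for sizing a later trial, and an odds ratio diluted by pre-dose cases would understate the effect in patients at risk.

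**Working it through.** **Inputs from section 9.2:** control rate 0.445, thiamine rate 0.155, 30 evaluable per group, one-sided 0.05, chi-squared test, literature range for control incidence 43–73%. **Assumed, not in the documents:** the share q delirious before the first dose, taken as 2%, 5% and 10% and equal in both arms. That is 30q = 0.6, 1.5 and 3 patients per arm.

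**Step 1: the plan's own figure.** The odds ratio is (0.155/0.845)/(0.445/0.555) = 0.2288. With mean rate 0.300, the pooled-variance normal formula gives

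Φ[(0.290 − 1.645·√(2·0.3·0.7/30)) / √((0.445·0.555 + 0.155·0.845)/30)] = Φ[(0.2900 − 0.1946)/0.1122] = Φ(0.850) = 80.2%.

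The stated 80% reproduces. Exact power, which sums the binomial probabilities of every pair of counts for which the same test rejects, is 81.1%. Exact power is used from here on.

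**Step 2: control total held at 0.445, odds ratio acting only on patients at risk.**
- At-risk control rate: c = (0.445 − q)/(1 − q)
- At-risk thiamine rate: t = 0.2288·o/(1 + 0.2288·o), where o = c/(1 − c)
- Thiamine total: T = q + (1 − q)·t

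Example, q = 5%: c = 0.395/0.95 = 0.416; o = 0.712; t = 0.1628/1.1628 = 0.140; T = 0.05 + 0.95·0.140 = 0.183. The odds ratio on totals becomes (0.183/0.817)/(0.445/0.555) = 0.279, with no change in what the drug does.

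**Step 3: pre-dose cases added on top of both planned rates.** Control total q + (1 − q)·0.445; thiamine total q + (1 − q)·0.155.

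**Step 4: pre-dose cases left out and replaced.** 30 at-risk patients per arm, with rates c and t from step 2.

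| q (assumed) | Step 2 totals | Step 2 power | Step 3 totals | Step 3 power | Step 4 power |
|---|---|---|---|---|---|
| 0 | 0.445 v 0.155 | 81.1% | 0.445 v 0.155 | 81.1% | 81.1% |
| 2% | 0.445 v 0.166 | 77.6% | 0.456 v 0.172 | 78.2% | 80.5% |
| 5% | 0.445 v 0.183 | 71.8% | 0.473 v 0.197 | 73.8% | 79.6% |
| 10% | 0.445 v 0.212 | 61.0% | 0.501 v 0.240 | 66.9% | 77.5% |

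**Step 5: higher control incidence.** The step 2 formulas, with 0.445 replaced by another total from the plan's range:

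| Control total | q = 0 | q = 5% | q = 10% |
|---|---|---|---|
| 60% | 85.9% | 81.2% | 75.5% |
| 73% | 86.3% | 83.4% | 80.0% |

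At q = 5% the loss is about 9 points at a control rate of 44.5%, 5 points at 60% and 3 points at 73%.

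**The case against.** **The gap may be short.** The synopsis speaks of a rating immediately before transplant. The rationale for Amendment 6 was to gain time for insurance authorisation ahead of randomisation, which suggests early consent and later randomisation. A reader might infer that patients are rated and randomised as outpatients, well before conditioning. The documents do not support that: they permit early enrolment, but they neither describe a conditioning schedule nor say that randomisation is early. What stands is that no maximum interval is set, and that the time from transplant to first dose is unchecked even on the shortest reading.

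**The stated power is not wrong.** Section 9.2 gives its rates as totals in the evaluable groups. Taken literally, power remains 80% whatever the share of early cases. Early cases then mean that the drug must do more among patients at risk: at q = 5%, 0.416 against (0.155 − 0.05)/0.95 = 0.111, an odds ratio of 0.17. This is fair. The loss in step 2 depends on applying 0.229 to patients at risk, and the range for q has no source.

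**All-event counting is a legitimate policy.** The primary objective (2.1.1) is incidence during the transplant hospitalisation, and early cases are balanced in expectation. A reader might infer that the result no longer measures prevention. That is too strong: the test keeps its error rate and the estimate is attenuated, not invalid.

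**The remedy has a price.** Section 7.11 replaces patients for missed doses or ratings only, so a new criterion is needed. Staff may be unavailable before a first infusion, and even the daily ratings of delirious patients are limited to weekdays as scheduling allows. These points stand and shape the fix.

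**Conclusion.** The gap is real. One check before randomisation, no limit on the interval to dosing, a day-1 rating with no stated order, and an endpoint without an onset condition together mean that delirium present before dosing is counted as a primary event. The consequence is dilution toward no effect, not bias in favour of either arm.

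The size cannot be fixed from the documents. At an assumed 2% the loss is about 3 points of power. At 5% it is about 7 to 9 points, and at 10% about 14 to 20 points, depending on whether the cases are added on top of the planned rates or contained in the 44.5%. It is smaller if control incidence is well above 44.5%, which lies near the bottom of the plan's own range.

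Three limits apply. An episode that resolved before the day-1 look-back would not be seen. A delirious patient who receives too few doses leaves the efficacy set anyway. With 0.6 to 3 such patients expected per arm, chance imbalance between arms is also possible.

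**What to change.** 1. **Timing (7.1, 7.4).** Do the day-1 DRS before the first infusion, and record the time of both. Dosing should not depend on the rating being done or on its result.
2. **Primary event (3.1, 7.11, 9.1).** Define it as the first DRS above 12 on an assessment after the pre-dose one, among patients whose pre-dose DRS was 12 or less. If the next rating is at least a day after the first infusion, its 24-hour look-back is clear of the pre-dose period.
3. **Efficacy set (7.11, 9.1).** Add a pre-dose DRS above 12 as an explicit criterion, applied blind in both arms, for leaving the primary efficacy set and being replaced. Status measured before the first blinded infusion cannot be affected by treatment, so this adds no treatment-related selection.
4. **Missing pre-dose rating.** Keep these patients in the set and count any DRS above 12 from day 1. Some dilution remains, but availability of raters does not decide who is analysed.
5. **Sensitivity analysis (9.3).** Compare all randomised patients, with every DRS above 12 counted.

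Under the step 2 assumptions, items 2 and 3 restore exact power to 80.5%, 79.6% and 77.5% at q = 2%, 5% and 10%. The cost is an amendment to the endpoint and evaluability text, some scheduling effort on day 1, and a few patients who leave the primary count and must be replaced. No new assessment is needed.

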3.2 Secondary Endpoints

3.2.1 Delirium duration will be measured in days and delirium severity will be defined as the highest DRS score recorded. If delirium occurs, frequency of assessment will increase to daily, Monday through Friday, as scheduling permits, until delirium resolves.

3.2.2 We will examine the relationship between thiamine levels at the end of the seven day intervention period and the development of delirium at any point during the post-transplant hospitalization.

3.2.3 Scores on FACT-BMT, PROMIS-D, PTSS-14, ECOG-PS, and MOCA will be measured at one, three, and six months after transplant.

4.0 PATIENT ELIGIBILITY

In order to participate in this study a subject must meet ALL of the eligibility criteria outlined below.

4.1 Inclusion Criteria

Eligible subjects must meet all of the following criteria to be enrolled in the study:

4.1.1 Admission or planned admission to the UNC Hospital Bone Marrow Transplant Unit for allogeneic stem cell transplant.

4.1.2 At least 18 years of age.

4.1.3 Able to speak English.

4.1.4 Able to provide informed consent.

4.2 Exclusion Criteria

Eligible subjects must not have any of the following to be enrolled in the study:

[figure not shown]
4.2.1 A history of adverse reaction to IV thiamine

4.2.2 Pregnancy, confirmed by a negative pregnancy test within 30 days of study enrollment

5.0 TREATMENT PLAN

5.1 Schema

Figure 1: Randomized controlled trial evaluating the efficacy of high dose intravenous thiamine for prevention of delirium in allogeneic hematopoietic stem cell transplantation.

- a. High dose IV thiamine in intervention group only (N=30)
- b. MOCA, FACT-BMT, PROMIS-D, PTSS-14, ECOG-PS
- c. DRS
- d. Thiamine levels weekly

5.2 Treatment Dosage and Administration

Subjects in the intervention group will receive thiamine 200 mg IV tid for seven days beginning on the day after of transplant. Subjects in the control group will receive 100 mL (equivalent volume to intervention) normal saline IV tid for seven days beginning on the day after transplant. All investigators will be blinded to which patients are assigned to which arm of the study. Only the Investigational Drug Service (IDS) will be aware of which patients will be assigned to which arms. At any time, the PI, primary medical providers, or other emergency personnel may request unblinding of a subject’s randomized treatment from IDS. If there is an adverse reaction, subjects will be treated symptomatically and consideration will be given to stopping the medication, as outlined in Section 5.3.

REGIMEN DESCRIPTION				
Group	Agent	Dose	Route	Schedule
Intervention	Thiamine	200 mg Thiamine HCL solution in 100 mL infusion bag of 0.9% Sodium Chloride	IV over 30 minutes (50 ml/hr)	Post-transplant Days 1 – 7 three times daily

Control	Normal Saline	100 mL of 0.9%	IV over 30 minutes (50 ml/hr)	Post-transplant Days 1 – 7 three times daily
---------	---------------	----------------	-------------------------------	--

Prescribing Information

Full prescribing information for thiamine can be found at the following web address: http://editor.fresenius-kabi.us/Pis/Thiamine_Inj_45819E_May_08.pdf

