Editorial, administrative changes

- (1) The version date was updated throughout the protocol
- (2) In Sections 5.8 and 7.5 we have broadened allowable methods of follow-up assessment to include mail, in addition to in person assessment and over the phone.
- (3) All personnel, except for the Principal Investigator, Co-Investigators, and Biostatistician have been removed from the cover sheet to limit future protocol amendments related only to staff changes, as recommended by the Protocol Review Committee Compliance Coordinator
- (4) A minor error in Table 7.1 was corrected. Specifically, in the legend “c.” was previously incorrectly attributed to the DRS and “d.” to the longitudinal measures.
- (5) Throughout the protocol, we have modified the delirium assessment schedule to specify that delirium assessments will be performed at one, three, and six months after transplant for patients who develop delirium in the inpatient phase. This modification was made to ensure that delirium has resolved before completion of longitudinal follow-up measures.
- (6) Throughout the protocol, we have modified plan to continue recruitment until we have 60 *evaluable* participants to account for subjects who do not meet criteria for efficacy analysis (as described in Section 7.11) and will subsequently be replaced.

Scientific changes

- (1) In Section 7.11 we have modified the requirements for efficacy assessment to stipulate that patients must have delirium assessed at least weekly during hospitalization, until any of the following have occurred: 1.) they develop delirium (primary endpoint); 2.) they are discharged; or 3.) they reach 30 days post-transplant.

Therapy changes

- (1) Throughout the protocol, the preparation of our intervention was changed from Thiamine 200 mg diluted in 25 mL 0.9% normal saline to Thiamine 200 mg diluted in 100 mL 0.9% normal saline. Our placebo was changed from 25 mL 0.9% normal saline to 100 mL 0.9% normal saline to maintain blinding. The intervention will be administered over 30 minutes. No changes were made to strength, route (intravenous), frequency (TID), or duration (seven days). This modification was made in response to the nation-wide IV bag shortage following the hurricane in Puerto Rico. This modification in no way increases risk to subjects.

***THE ATTACHED VERSION DATED 9/4/18 INCORPORATES THE ABOVE
REVISIONS***

ATTACH TO THE FRONT OF EVERY COPY OF PROTOCOL

PROTOCOL AMENDMENT # 3

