6.1.3 How Supplied

The drug will be obtained from commercial supply through UNC Pharmacy and UNC Investigational Drug Service (IDS).

Full prescribing information for (Thiamine) is available at:

http://editor.fresenius-kabi.us/Pis/Thiamine_Inj_45819E_May_08.pdf

6.1.4 Dosage and Administration:

Subjects in the intervention group will receive Thiamine 200 mg IV tid.

6.1.5 Storage and Stability:

Thiamine should be stored at room temperature (between 68° to 77° F).

6.1.6 Handling and Disposal: Local requirements for disposal of hazardous drugs will be followed.

Please see UNC policy on hazardous drugs:

<http://news.unchealthcare.org/empnews/att/2011/nov/admin0188/>.

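### The Section 5.2 regimen table gives an infusion rate four times too low in both arms: 100 mL over 30 minutes needs 200 mL/h, not 50 mL/h

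*Combined protocol and SAP*

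**What the plan says.** Section 5.2 of the combined protocol and SAP holds the administration instruction for study drug and placebo.

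- **Thiamine arm, volume:** the regimen table specifies "200 mg Thiamine HCL solution in 100 mL infusion bag of 0.9% Sodium Chloride".
- **Control arm, volume:** the text says "Subjects in the control group will receive 100 mL (equivalent volume to intervention) normal saline IV tid for seven days", and the control row of the table also gives 100 mL.
- **Time and rate, both arms:** each row reads "IV over 30 minutes (50 ml/hr" (bracket closed in the original), three times daily on post-transplant days 1 to 7.

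Section 6.1.4 repeats the dose, "Subjects in the intervention group will receive Thiamine 200 mg IV tid", without a volume, time or rate. No other current section gives an infusion rate or says which figure prevails if they conflict.

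Two further places bear on the point. Section 7.11 defines who is evaluable for efficacy partly by dose count: "a patient must receive at least 17/21 (80%) thiamine doses". The log entry for Amendment 4 records the last listed change of preparation, "from Thiamine 200 mg diluted in 25 mL 0.9% normal saline to Thiamine 200 mg diluted in 100 mL 0.9% normal saline", the matching change of placebo, and "The intervention will be administered over 30 minutes".

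**The concern.** Volume, duration and rate are tied together, so any two fix the third. In this table they disagree. A full bag can be given on time or at the printed rate, but not both. Section 10.5 requires the study to be run exactly as the approved protocol describes, and for this item that is impossible.

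A rate in mL/h is a figure that could go straight into a pump. At stake is what each patient received: the full dose in half an hour, the full dose over a much longer infusion or, less plausibly, part of the dose. The concern is with delivery of the regimen. It does not touch the endpoint, the sample size or the analysis.

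**Working it through.** **Inputs**

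| Quantity | Value | Source |
|---|---|---|
| Volume per infusion, both arms | 100 mL | Section 5.2, text and table |
| Thiamine per bag | 200 mg | Section 5.2 table; Section 6.1.4 |
| Duration, both arms | 30 min = 0.5 h | Section 5.2 table |
| Stated rate, both arms | 50 mL/h | Section 5.2 table |
| Infusions | 3 per day for 7 days = 21 | Section 5.2; Section 7.11 |
| Superseded volume | 25 mL | Amendments 2 and 4 |

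**Step 1. Try to reproduce the stated rate.** Rate = volume / time.

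- Current volume: 100 mL / 0.5 h = 200 mL/h. This does not reproduce 50 mL/h; 200 / 50 = 4.
- If 2 mL of drug is added to the thiamine bag (an assumption, taken from the 2 mL syringe described under Amendment 1): 102 mL / 0.5 h = 204 mL/h, or 4.08 times the stated rate. The conclusion is unchanged.
- Superseded volume: 25 mL / 0.5 h = 50 mL/h. This reproduces the stated rate exactly.

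**Step 2. Decide which figure is wrong.** The table alone shows a contradiction without saying which number is at fault. The surrounding text points to the rate. The 100 mL volume appears in the prose and in both rows. The 30 minutes is the main entry in its cell, with the rate only in brackets after it. The Amendment 4 entry states 100 mL and 30 minutes together. It also says of the placebo: "Our placebo was changed from 25 mL 0.9% normal saline to 100 mL 0.9% normal saline to maintain blinding". That the 50 mL/h survived from the 25 mL period is an inference from Step 1; the documents do not say so.

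**Step 3. If 50 mL/h is programmed and the bag runs to the end.**

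- Time per infusion: 100 mL / 50 mL/h = 2 h, against 0.5 h.
- Per day: 3 × 2 h = 6 h, against 3 × 0.5 h = 1.5 h; 4.5 h more.
- Per course: 21 × 2 h = 42 h, against 21 × 0.5 h = 10.5 h; 31.5 h more per patient.

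**Step 4. If 50 mL/h is programmed and the pump is stopped at 30 minutes.**

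- Volume given: 50 mL/h × 0.5 h = 25 mL.
- Thiamine given: (25 / 100) × 200 mg = 50 mg, a quarter of the dose and below the 200 mg three times daily by which Section 1.2 defines high dose.

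This second case is unlikely, because each bag is specified as one 200 mg dose. If it did happen, the 17-of-21 rule would not reveal it, since that rule counts doses and not the volume or milligrams given.

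**The case against.** The best counter-argument concerns weight, because the arithmetic is not in dispute. The dose is unambiguous, the wrong figure is a bracketed gloss, and the text and Amendment 4 make the intended volume and time fairly plain. A nurse reading the cell sees 30 minutes first. The documents do not show that pumps are set from this table, and the pharmacy order and bag label are not included. The extra hours therefore depend on staff choosing the rate over the time printed beside it.

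The documents also give little sign that infusion speed matters. The regimen began as a four-minute injection and moved to 30 minutes for nursing workflow, and Section 6.1.7 describes rapid injection of 100 mg with few side effects. On this view the point is an editorial slip.

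Much of that stands. The consequences are conditional, the partial-dose case should carry little weight, and the documents do not show that any patient was infused at the wrong rate. The safety evidence concerns faster delivery and does not address a 2-hour infusion, but nothing ties efficacy to 30 minutes either. What the objection does not remove is that the operative dosing table cannot be followed as written. Readers can probably infer the intended rate, but they should not have to infer a pump setting.

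**Conclusion.** The concern holds. The stated rate is a quarter of what the stated volume and time require: 50 mL/h against 200 mL/h, in both arms. The contradiction rests on Section 5.2 alone and needs no assumption. Naming the rate as the wrong figure rests on the repeated 100 mL volume, the 30-minute main entry and the Amendment 4 log.

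The practical effect ranges from none, if staff follow volume and time, to an extra 31.5 hours of infusion per patient, if they programme the printed rate and complete all 21 bags. The error is identical in both arms, so it does not by itself unblind or bias the comparison, and it does not affect the sample size. No safety or efficacy effect of slower infusion is claimed. It should be fixed because it sits in the administration instruction for study drug and placebo, but it is not critical.

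**What to change.** Change the rate to 200 mL/h in both rows of the Section 5.2 table. If 50 mL/h is in fact intended, keep it and state a 2-hour infusion in both rows. Then check pharmacy or nursing infusion records to confirm that full bags were given. If dosing is already complete, the records check and a corrected regimen description are still worth having, because they establish what was delivered in each arm.

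The cost is one figure in each of two table rows and a review of existing records. No new patients, procedures or data collection are needed.
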